5.5.2 Power for secondary outcomes

785 total enrolled women with 408 pregnancy outcomes (102 for Cohort A, 204 for Cohort B1, and 102 for Cohort B2) will have the following power to rule out a difference represented by the risk ratios presented below [Table 4] for each of the secondary outcomes.

QUVIVIQ® (daridorexant) Insomnia disorder ID-078A403 Version 4 23 October 2023, page 46/90

Confidential

 Table 4
 Power estimates for secondary outcomes

Secondary outcome category ^a	Secondary outcome ^b	P _B (B, B1 and B2)	P _A ^c	Risk ratio	NI margin	Power for A vs B1	Power for A vs B2	Power for A vs B	
To the state of th		4.6%	4.83%	2.5	6.9%	95.5%	88.4%	97.4%	
Pregnancy complications	Preeclampsia ^d			3	9.2%	> 99.9%	98.8%	> 99.9%	
				3.5	11.50%	> 99.9%	>99.9%	> 99.9%	
D	II			2.5	4.5%	83.2%	71.0%	87.6%	
Pregnancy complications	Hypertensive disorders ^e	3.0%	3.15%	3	6.0%	97.6%	92.2%	98.7%	
	G 1551 G 51			3.5	7.50%	> 99.9%	98.9%	> 99.9%	
D			3.15%	2.5	4.5%	83.2%	71.0%	87.6%	
Pregnancy complications	Preterm labor ^f	3.0%		3	6.0%	97.6%	92.2%	98.7%	
				3.5	7.50%	> 99.9%	98.9%	> 99.9%	
n.		1 4.4%	4.62%	2.5	6.6%	94.6%	86.5%	96.7%	
Pregnancy complications	Gestational diabetes ^g			3	8.8%	> 99.9%	98.5%	> 99.9%	
complications	diabetes			3.5	11.00%	> 99.9%	>99.9%	> 99.9%	
	Elective or				2.5	27.0%	> 99.9%	>99.9%	> 99.9%
Pregnancy outcomes	therapeutic pregnancy	18.0%	18.90%	3	36.0%	> 99.9%	>99.9%	> 99.9%	
outcomes	terminations ^h			3.5	45.00%	> 99.9%	>99.9%	> 99.9%	
			11.55%	2.5	16.5%	> 99.9%	>99.9%	> 99.9%	
Pregnancy outcomes	Spontaneous abortions ⁱ	11.0%		3	22.0%	> 99.9%	>99.9%	> 99.9%	
outcomes				3.5	27.50%	> 99.9%	>99.9%	> 99.9%	
	Fetal death or stillbirth ^j	1.4%	1.47%	2.5	2.1%	50.8%	39.8%	56.0%	
Pregnancy outcomes				3	2.8%	75.9%	62.9%	81.0%	
outcomes				3.5	3.50%	91.7%	82.0%	94.6%	

QUVIVIQ® (daridorexant) Insomnia disorder ID-078A403 Version 4 23 October 2023, page 47/90

Confidential

Secondary outcome category ^a	Secondary outcome ^b	P _B (B, B1 and B2)	P _A ^c	Risk ratio	NI margin	Power for A vs B1	Power for A vs B2	Power for A vs B
_		62.0%	60.1%	2.5	93.00%	> 99.9%	>99.9%	> 99.9%
Pregnancy outcomes	Live birth ^{c,k}			3	124.00%	> 99.9%	>99.9%	> 99.9%
outcomes				3.5	155.00%	> 99.9%	> 99.9%	> 99.9%
.				2.5	16.5%	> 99.9%	> 99.9%	> 99.9%
Pregnancy outcomes	Premature birth ¹	11.0%	11.55%	3	22.0%	> 99.9%	> 99.9%	> 99.9%
outcomes				3.5	27.50%	> 99.9%	> 99.9%	> 99.9%
) () () () () () () () () () (2.10%	2.5	3.0%	39.5%	30.9%	43.7%
Infant outcomes	Minor congenital malformations ^m	2.0%		3	4.0%	62.5%	50.2%	67.8%
	mariormations			3.5	5.00%	81.7%	69.5%	86.1%
	Small for gestational age ⁿ	10.0%	10.50%	2.5	15.0%	97.7%	92.7%	98.8%
Infant outcomes				3	20.0%	> 99.9%	> 99.9%	> 99.9%
				3.5	25.00%	> 99.9%	> 99.9%	> 99.9%
	Low birth weight ^o	8.5%	8.93%	2.5	12.8%	95.1%	87.7%	97.0%
Infant outcomes				3	17.0%	> 99.9%	98.7%	> 99.9%
				3.5	21.25%	> 99.9%	> 99.9%	> 99.9%
	Infant death ^p	2.9%	3.05%	2.5	4.4%	53.5%	42.3%	58.5%
Infant outcomes				3	5.8%	78.6%	66.1%	83.3%
				3.5	7.25%	93.3%	84.7%	95.7%
	TT '. 1' .'	2.0%	2.10%	2.5	3.0%	39.5%	30.9%	43.7%
Infant outcomes	Hospitalizations for serious illness ^q			3	4.0%	62.5%	50.2%	67.8%
				3.5	5.00%	81.7%	69.5%	86.1%

Confidential

23 October 2023, page 48/90

Secondary outcome category ^a	Secondary outcome ^b	P _B (B, B1 and B2)	P _A ^c	Risk ratio	NI margin	Power for A vs B1	Power for A vs B2	Power for A vs B
	Postnatal growth and development ^{c,r}	6.0%	6.30%	2.5	9.0%	85.0%	73.4%	89.0%
Infant outcomes				3	12.0%	98.1%	93.6%	99.0%
				3.5	15.00%	> 99.9%	> 99.9%	> 99.9%

^a The total population of enrolled patients (n = 785) was used to estimate the power for the secondary outcomes in the pregnancy complications and pregnancy outcomes categories. The number of pregnancy outcomes (n = 408) was used to estimate the power for the secondary outcomes in the infant outcomes category.

NI = non-inferiority; $P_A = prevalence$ in Cohort A; $P_B = prevalence$ in Cohort B.

^b Only live births were considered positive outcomes. All other outcomes were considered negative. Because the assumed rate of live birth in Cohort B is high (62%), the estimated rate of live birth in Cohort A for risk ratios of 2.5 or higher corresponds to a rate below 0%, which is not realistic. Therefore, the estimated power is >99.9%.

^c For negative outcomes, the assumed prevalence in Cohort A is $P_A = 1.05 \cdot P_B$. For positive outcomes, the assumed prevalence is $P_A = 1 - ((1 - P_B) \cdot 1.05)$.

d Source data: [Abalos 2013]

^e Source data: [Turner 2017]

f Source data: [Danforth 2008]

g Source data: [Behboudi-Gandevani 2019]

h Source data: [Jones 2017]

ⁱ Source data: [Ammon Avalos 2012]

^j Source data: [Hug 2021]

k Source data: [Ventura 2000]

¹ Source data: [Walani 2020]

^m Source data: [Chimah 2022]

ⁿ Source data: [Sclaudecker 2017]

Source data. [Sciaduceker 2017

^o Source data: [Osterman 2023]

p Source data: [who.int]

^q Source data: [McLaughin 2022]

^r Source data: [Valla 2015]

23 October 2023, page 49/90

Confidential

5.6 Data management

5.6.1 Data collection

The reporter of information can be the patient, patient's HCPs, or infant's HCP, where applicable [see Figure 1]. This information includes all data collection elements described in Section 5.3. Where the HCP is unavailable, the patient can report the necessary information to the CC research staff for entry into the eCRF. Where there is a discrepancy in the information reported by the patient and the HCP, the HCP-reported information will take precedent. In particular, the insomnia diagnosis and history will be collected from both the patient and the HCP (i.e., preferably not the obstetrician or nurse midwife). However, if the HCP cannot be reached to confirm the insomnia diagnosis and history, the patient is considered a suitable source for reporting insomnia history characteristics.

5.6.1.1 Baseline

The baseline information and any data up to the point of enrollment will be collected at the enrollment encounter. Baseline information will be collected to confirm patient eligibility, collect relevant medical history, and characterize the current pregnancy status of the patient. The following data elements will be collected at baseline:

General

- Identification number.
- Contact details of HCP at initial contact with the registry.
- Date of initial report.
- Documentation of informed consent/assent.
- Reporter of information (e.g., patient, HCP).
- Inclusion/exclusion criteria.

• Maternal Information

- Age of patient (mother) at conception.
- Patient demographics and characteristics: height, pre-pregnancy and current pregnancy weight, education, BMI, race, ethnicity (if permitted by local regulations).
- Medical history: genetic disorder, previous pregnancies and their outcome (parity, gravidity, previous preterm births, previous spontaneous abortions or elective or therapeutic terminations, reasons for any elective or therapeutic termination, history of congenital malformations), hypertension, diabetes, seizure disorder, autoimmune disease, lifetime history of psychiatric diseases (e.g., major depression, anxiety, psychotic diseases), known risk factors for adverse pregnancy outcomes including exposures to known teratogens [Appendix 2], history of oncologic disorders, and any previous exposure to chemotherapy and radiotherapy.

23 October 2023, page 50/90

Confidential

- Insomnia history including but not limited to the earliest insomnia diagnosis date and duration of insomnia.
- Family reproductive history (e.g., multiple births, pregnancy complications [i.e., preeclampsia, pregnancy-induced hypertension, preterm labor, gestational diabetes, placenta previa], congenital malformations, spontaneous abortions, premature births, chromosomal abnormalities, evidence of developmental delays).
- Paternal Information (to be reported by the mother)
 - Demographics and characteristics: height, weight, BMI.
- Current pregnancy
 - Date of the LMP.
 - Ultrasound results for gestational dating.
 - Prenatal test results (e.g., rubella titer, toxoplasmosis, venereal disease research laboratory test, hepatitis screen, ultrasounds, amniocentesis, maternal serum alpha-fetoprotein screen, glucose screen).
 - Number of fetuses.
 - Complications during pregnancy (including any adverse drug reaction).
 - Illness during pregnancy (e.g., virus infection).
 - QUVIVIQ exposure (start/stop date, dosage, frequency, reason for discontinuation, if applicable).
 - Other medication or biological product exposures, including other insomnia medications, prescription drugs, over-the-counter products, supplements (start/stop date, dosage, frequency, indication).
 - Substance use (e.g., tobacco, alcohol, illicit drugs, marijuana, caffeine consumption).
 - Chemicals and environmental hazards (e.g., radiation).
 - AEs that occurred from the date of the LMP to study enrollment: patient AEs and SAEs in Cohort A (following QUVIVIQ exposure) and in the Cohort B including event, start date, ongoing or end date, seriousness, severity, relationship to QUVIVIQ, outcome, hospitalization, duration or hospitalization, and action taken.

5.6.1.2 Study follow-up

Women will be followed from enrollment through the end of their pregnancy and up to 52 weeks after the infant's birth. Infants will be followed for 52 weeks after birth. Maternal outcomes during the postpartum follow-up year (aside from safety surveillance and lactation information from breastfeeding mothers) will not be collected. Specific data to be collected during different periods during follow-up are detailed below. Safety reporting will be ongoing throughout the duration of the study.

Confidential

5.6.1.2.1 During pregnancy follow-up (estimated at approximately 14, 21, and 34 weeks gestation)

- Date of contact.
- Reporter of information (e.g., patient, HCP, other).
- Current weight.
- Changes in lifestyle risk factors (e.g., smoking, caffeine, alcohol use, illicit drug use, marijuana use).
- Insomnia information including but not limited to insomnia improvement.
- Changes in comorbid conditions.
- QUVIVIQ treatment: start and stop dates, dose, dosing frequency, reason for discontinuation, if applicable.
- Current medication (including other insomnia treatments, over-the-counter medications, folic acid and other vitamins, herbal remedies or supplements, vaccinations, or other medication use to treat chronic conditions or comorbidities): start and stop dates, dose, dosing frequencies.
- Ultrasound results for gestational dating.
- Prenatal test results.
- Pregnancy outcome: live births, spontaneous abortions, stillbirths, elective or therapeutic terminations, and autopsy results and pathology reports, if available.
- Reason for elective or therapeutic termination: prenatal testing finding, risk to mother's health, or undesired pregnancy.
- Congenital malformations noted: description and attribution.
- Patient AEs and SAEs in Cohort A and in Cohort B: event, start date, ongoing or end date, seriousness, severity, relationship with QUVIVIQ, hospitalizations, duration of hospitalization, outcome, and action taken.

5.6.1.2.2 *At delivery*

- Reporter of information (name and position).
- Pregnancy outcome: live births, spontaneous abortions, stillbirths, elective or therapeutic terminations.
- Reason for elective or therapeutic termination: prenatal testing finding, risk to mother's health, or undesired pregnancy.
- Autopsy results and pathology reports, if available.
- Mode of delivery: vaginal delivery, assisted delivery / cesarean section, type of anesthesia.
- Insomnia information including but not limited to insomnia improvement.

23 October 2023, page 52/90

Doc No D-23.335

Confidential

- Changes in comorbid conditions.
- QUVIVIQ treatment: start and stop dates, dose, dosing frequency, reason for discontinuation, if applicable.
- Current medications (any other insomnia treatments, folic acid and other vitamins, herbal remedies or supplements, vaccinations, or other medications used to treat chronic conditions or comorbidities): start and stop dates.

 - Infant characteristics: postnatal growth and development, feeding behavior, weight, length, head circumference, breastfeeding status (if infant is breastfed, if the mother was exposed to QUVIVIQ), vaccine information, current medications.
 - Evidence of any new congenital malformations and growth alterations since the last follow-up.
 - Patient or infant AEs and SAEs in Cohort A and in Cohort B: event, start date, ongoing or end date, seriousness, severity, relationship with QUVIVIQ, hospitalization, duration of hospitalization, outcome, and action taken.

• Termination status

- Completion of follow-up.
- Early termination/withdrawal (including date of withdrawal, reason for withdrawal).

 QUVIVIQ treatment, current medications (including insomnia medications), pregnancy status, and infant characteristics (for live births), and safety events will be collected similarly as during study follow-up.

5.6.2 Data management

IQVIA, the CRO, will be responsible for the data management of this study. This includes designing the eCRFs with input and final approval from Idorsia, as well as quality checking the accuracy, completeness, and timeliness of data recorded. The CRO will produce a Data Management Quality Plan and a Data Cleaning Plan that describes the quality checking to be performed on the data. Data quality will be enhanced through a series of programmed data quality checks that automatically detect out-of-range or anomalous data. In the event of discrepant data, the CRO will request data clarification from the CC research staff, which the CC research staff will resolve by providing answers in the EDC system.

Idorsia will perform oversight of the data management of this study, including the approval of the data management plans and guidance.

The CC, which contains a PI and research staff, will be responsible for data entry into the EDC system. The CC research staff will receive training for reviewing the ICF process with the patient and entering data in the eCRF. The CC research staff will have access to a manual for appropriate eCRF completion. All eCRFs should be completed by designated, trained CC research staff. eCRFs will be reviewed and electronically signed and dated by the PI. In the US, a senior epidemiologist will assume the role of PI, ex-US countries will designate a PI from a site (e.g., HCP).

[figure not shown]
When permitted by local regulations, patients will also have the option to directly enter data into the eCRF through the website-associated app.

eCRFs and correction documentation will be maintained in the EDC system audit trail. System backups for data stored at the CRO and records retention for the study data will be consistent with the CRO standard procedures. The CRO will comply with Idorsia's procedures regarding archiving and record management.

23 October 2023, page 55/90

Doc No D-23.335

Confidential

CC = Coordinating center; CRO = Contract Research Organization; EDC = electronic data capture; HCP = healthcare provider (e.g., primary care provider, insomnia specialist, psychiatrist, obstetrician, nurse midwife, infant's pediatrician, other).

5.6.3 Source documents

In most cases, the source documents are contained in the patient's medical record and data collected on the eCRF must match the data in the medical records. In some cases, the eCRF, or part of the eCRF, may also serve as a source document. In these cases, a document should be available at the investigator's site and clearly identify the data that will be recorded in the eCRF, and for which the eCRF will stand as the source document. All original source documentation is expected to be stored at the site for the longest possible time required by applicable local regulations.

5.6.4 File retention and archiving

To enable evaluations and/or audits from regulatory authorities or Idorsia, the investigator agrees to keep records, including the identity of all participating patients, all original signed ICFs, copies of all eCRFs, SAE forms, source documents, and adequate documentation of relevant correspondence (e.g., letters, meeting minutes, telephone call reports). The records should be retained by the investigator according to local regulations, or as specified in the study contract, whichever is longer.

Each site will receive a study site file at study initiation containing all documents necessary for conducting the registry which will be updated throughout the study. This file must be available for review if the site is selected for monitoring, audits, or inspections, and must

be safely archived for at least 5 years after the completion of study participation. Documents to be archived include the patient enrollment log and the signed ICF. If archiving the file is no longer possible at the site, the site is instructed to notify Idorsia.

5.6.5 Changes to the protocol

Changes to the protocol will be documented in written protocol amendments. Major (i.e., substantial or significant) amendments will usually require submission to the relevant IEC/IRB for approval or favorable opinion and the FDA and/or Competent Authorities. In such cases, the amendment will be implemented only after the approval or favorable opinion has been obtained.

Minor (non-substantial) protocol amendments, including administrative changes, will be filed at each participating site and will be submitted to the relevant IEC/IRB or regulatory authorities where required by pertinent regulations. Any amendment that could have an impact on the patient's agreement to participate in the study requires the patient's informed consent prior to continued participation in the study.

5.7 Data analysis

5.7.1 Planned analysis

5.7.1.1 Interim enrollment assessment

Regular study updates will be provided in alignment with required safety reporting requirements and are anticipated annually. At 5 years following the first patient enrollment, an interim analysis will be conducted to assess enrollment and target sample size assumptions, and any needed modifications to patient recruitment and/or retention efforts will be evaluated. A report which summarizes the number of patients enrolled and QUVIVIQ exposure classification information among prospective pregnancies (the proportion of Cohort A vs Cohort B1) and describes primary and secondary outcome data will be included as part of the interim analysis.

5.7.1.2 Final analysis

A final study report will be generated after all data collection is complete, or the study is otherwise terminated, including up to 21 months of follow-up for enrolled women with their child. The final report will encompass all planned analyses, including a description of the complete study population, as described in Section 5.2 and in the SAP.

Details and scope for the final analysis will be described in the SAP.

5.7.1.3 Primary analysis

The final primary analysis will be conducted once all data collection is complete, including up to 21 months of follow-up for enrolled patients. Only women with prospective pregnancies (i.e., outcome of the pregnancy is not known at time of enrollment) will be included in the primary analysis.

Confidential

The primary outcome for this study is major congenital malformations in infants. All other outcomes will be classified as secondary.

The primary analysis will use risk ratios (one-sided 97.5% CI) to compare major congenital malformations in infants between Cohort A and Cohort B1 among women with first trimester exposure to their respective insomnia medications. Women exposed to QUVIVIQ who take other medications for insomnia at any time during pregnancy will be excluded from the primary analysis. Women with known teratogen exposure during pregnancy will be included in the primary analysis. Sensitivity analyses will be conducted evaluating timing of exposure. Additional sensitivity analyses will be conducted, including women exposed to QUVIVIQ who were exposed to other insomnia medications, and excluding those with known teratogen exposure [Section 5.7.4.4].

Adjudicated major congenital malformations reported up to 1 year of age by the mother or by an HCP will be included in the primary analysis. Pregnant women who receive any prenatal screening after enrollment (post-enrollment) that provides knowledge of the pregnancy outcome will be included in the primary analysis. Decision criteria with regard to prenatal testing before enrollment (pre-enrollment) will be applied to the study population for inclusion in the primary analysis as follows: pregnant women with pre-enrollment prenatal testing who have not received the test results at the time of enrollment will be included in the primary analysis, while pregnant women who had prenatal testing pre-enrollment where the result is known prior to enrollment will be included or excluded from the primary analysis depending on the result of the test (see Table 5 for pertinent descriptions for inclusion in analyses based on timing and the results of prenatal screening tests).

Results from the following prenatal tests will be used to determine if a pregnancy will be included in the primary analysis: maternal serum screening, 18–20-week ultrasound, amniocentesis, chorionic villus sampling, and fetal magnetic resonance imaging. Additional screening tests for major congenital malformations that are adapted in clinical practice during the study period may also be used. Additional exploratory analyses will evaluate major congenital malformation risks among women with exposure in another trimester (e.g., the second and/or third trimester). Women who have received test results (regardless of what the results are) will be included in the primary analysis, except for:

- Women who have received first trimester prenatal screening in which either aneuploid disorders or genetic disorders that cause major congenital malformations have been detected, because these disorders are unrelated to medication use.
- Any prematurity-related disorders and transient conditions.

Table 5 Considered subpopulations of patient groups based on timing and result of prenatal screening tests for inclusion in analysis sets

Groups determined by test and result	Inclusion in analysis
Group 1 : Women who had prenatal testing prior to enrollment in registry where the result is known prior to enrollment	Inclusion in each analysis based on subgroup
Subgroup 1: Women who have normal prenatal screening findings	Included in primary analysis; sensitivity analysis of known test result(s) prior to enrollment
Subgroup 2: Women who have pregnancies with aneuploid disorders or genetic disorders that cause major congenital malformations	Excluded from primary and secondary analysis; analyzed as a separate group
Subgroup 3: Women who have pregnancies with results (normal or abnormal) that are unrelated to aneuploid disorders or genetic disorders that cause major congenital malformations	Included in primary analysis; included in sensitivity analysis of known test result(s) prior to enrollment
Group 2: Women who had no prenatal screening prior to enrollment in the registry	Included in primary analysis; included in sensitivity analysis of women who have pregnancies with aneuploid disorders or genetic disorders that cause major congenital malformations
Group 3 : Women who had prenatal screening prior to enrollment in the registry and result is not known prior to enrollment	Included in primary analysis; included in sensitivity analysis of women who have pregnancies with aneuploid disorders or genetic disorders that cause major congenital malformations

5.7.2 Planned method of analysis

5.7.2.1 General considerations

Descriptive analyses will be performed to gain an understanding of the qualitative and quantitative nature of the data collected and the characteristics of the sample studied. Continuous variables will be reported as mean (and standard deviation), median, minimum, maximum, and range where appropriate. Categorical variables will be summarized as number and proportion of the total study population, and by subgroups where appropriate.

Data analysis for major congenital malformations will be based on exposure to QUVIVIQ or treatments for insomnia within 5 half-lives prior to conception or the first trimester. The primary analysis set will exclude women who have received first trimester prenatal screening in which either aneuploid disorders or genetic disorders causing major congenital malformations have been detected, because these disorders are unrelated to medication use. Prematurity-related disorders and transient conditions will also be excluded from the analysis of major congenital malformations.

Confidential

Analyses for the secondary outcomes will be conducted overall (encompassing preconception [within 5 half-lives prior to conception] and the entire pregnancy) as well as separately for preconception and each trimester (first trimester: conception to 13^{+6} weeks' gestation; second trimester: 14^{+0} to 27^{+6} weeks' gestation; third trimester: $\geq 28^{+0}$ weeks' gestation) as sample size allows. See Appendix 4 for the outcome-specific exposure-windows that will be evaluated. Gestational age will be determined based on results from the first available ultrasound or the date of the LMP when an ultrasound is not available [ACOG 2017, EMA 2005].

If sufficient numbers are obtained, analyses will also be presented by the subgroups of maternal age, race/ethnicity, prior history of elective or therapeutic pregnancy termination status, prenatal screening result (positive vs negative), prenatal testing status (performed vs not performed), and other important risk factors [see Section 5.7.4.4].

Any patient who is enrolled in the Cohort A or Cohort B and then becomes exposed to any ORA during pregnancy will be addressed in the analysis depending on the medication, the timing of the exposure, and the outcome of interest.

All computations and generations of tables, listings, and data for figures will be performed using SAS® version 9.4 or higher.

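### The protocol gives two conflicting rules for when an aneuploid or genetic malformation leaves the primary analysis set, and both turn on test type or timing although the stated reason is aetiology.

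*Protocol*

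**What the plan says.** Two rules appear for the primary analysis set.

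**First-trimester detection.** The plan in section 5.7.2.1 is to "exclude women who have received first trimester prenatal screening in which either aneuploid disorders or genetic disorders causing major congenital malformations have been detected". Section 5.7.1.3, just before Table 5, includes women with test results whatever they show, with this exception: "Women who have received first trimester prenatal screening in which either aneuploid disorders or genetic disorders that cause major congenital malformations have been detected". Section 5.9.1.2 repeats the exclusion. The reason given in 5.7.1.3 and 5.7.2.1 is that these disorders have nothing to do with medication.

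**Known before enrollment.** Section 5.7.1.3 also says: "Pregnant women who receive any prenatal screening after enrollment (post-enrollment) that provides knowledge of the pregnancy outcome will be included in the primary analysis". Table 5 then sorts women as follows.
- Group 1: "Women who had prenatal testing prior to enrollment in registry where the result is known prior to enrollment". Within it, Subgroup 2 (aneuploid or genetic disorders) is "Excluded from primary and secondary analysis; analyzed as a separate group". Subgroup 1 (normal findings) and Subgroup 3 (results unrelated to such disorders, normal or abnormal) stay in.
- Group 2: "Women who had no prenatal screening prior to enrollment in the registry".
- Group 3: "Women who had prenatal screening prior to enrollment in the registry and result is not known prior to enrollment".
- Groups 2 and 3 both carry the entry "Included in primary analysis; included in sensitivity analysis of women who have pregnancies with aneuploid disorders or genetic disorders that cause major congenital malformations".

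The tests that 5.7.1.3 names as deciding inclusion go beyond first-trimester screening: they include amniocentesis, the 18-20-week ultrasound and fetal MRI. Section 5.7.4.2 defines the prevalence numerator as women with any adjudicated case and makes no distinction by aetiology.

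**The concern.** The two rules differ on two points: whether the result must precede enrollment, and whether only first-trimester screening counts or any prenatal test. A statistical analysis plan cannot follow both, and a choice made once cases are known would be post hoc.

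Neither rule matches its reason. If a trisomy is set aside because the drug cannot have caused it, that holds equally when it is found at 12 weeks, at 20 weeks or at birth. As written, the same disorder is a primary case or not according to which test found it and when the result was read. Any difference between Cohorts A and B1 in screening uptake or in gestational age at enrollment could then shift the compared prevalences with no drug effect. Enrollment before testing is only preferred (sections 5.2 and 5.4.5), and nothing in the protocol makes its timing equal across cohorts.

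**Working it through.** **1. Two test cases**

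| Case | 5.7.1.3 text on post-enrollment screening, and Table 5 | First-trimester wording (5.7.2.1; similar in 5.7.1.3 and 5.9.1.2) |
|---|---|---|
| (a) Enrolled at 8 weeks, untested; first-trimester screening at 12 weeks finds aneuploidy | Included (Group 2) | Excluded by 5.7.2.1 |
| (b) Second-trimester amniocentesis with an aneuploid result, known before enrollment | Excluded (Group 1, Subgroup 2) | Included: not first-trimester screening |
| (c) Genetic disorder first found at birth, no earlier positive test | Included, and counted under 5.7.4.2 | Included, and counted under 5.7.4.2 |

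Cases (a) and (b) are contradictions. Case (c) shows that neither rule carries out the aetiological reason.

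**2. The plan's own sample size (section 5.5.1)**

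Inputs: P_B1 = 3%, P_A = 3.15%, margin = 3% × 3.0 − 3% = 6 points, one-sided α = 0.025, power 80%, r = 2.

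N_A = (r+1)(z₀.₈₀ + z₀.₉₇₅)² × [P_A(1−P_A) + P_B1(1−P_B1)]/2 ÷ {r[(P_A−P_B1) − margin]²}

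= 3 × 7.849 × 0.029804 ÷ (2 × 0.0585²) = 102.5, so N_B1 = 205.1. The protocol has 102 and 204. Power at 102/204 by the same approximation is 79.8% (stated: 80.1%). The design reproduces within rounding. Expected cases are 102 × 0.0315 = 3.2 in A and 204 × 0.03 = 6.1 in B1.

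**3. Possible shift in prevalence**

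Let g be the share of malformations that are aneuploid or genetic, and s the share of those removed because the result was known before enrollment. The protocol gives neither. Assume g = 10-25%, with s = 60% in one cohort and 30% in the other, and a true prevalence of 3% in both. Ignoring the negligible change in the denominator, observed prevalence = 0.03(1 − g·s).

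- g = 10%: 2.82% versus 2.91%, difference 0.09 points, ratio 0.97 (inverse 1.03).
- g = 25%: 2.55% versus 2.775%, difference 0.225 points, ratio 0.92 (inverse 1.09).

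As a share of the 6-point margin this is 0.09/6 = 1.5% to 0.225/6 = 3.8%. The sign depends on which cohort is tested earlier. With equal s in both cohorts the ratio is 1.00. The expected number of cases removed from Cohort A is 102 × 0.03 × g × s, from 0.09 (g = 10%, s = 30%) to 0.46 (g = 25%, s = 60%).

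**4. Effect of an aetiology rule on the sample size**

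Section 5.4.4.1 describes the 3% background as covering structural or genetic defects. Taking the genetic share out, and keeping P_A = 1.05 × P_B1 and margin = 2 × P_B1 (risk ratio 3.0):

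| g | P_B1 | P_A | Margin | N_A | Power at 102/204 |
|---|---|---|---|---|---|
| 0 | 3.00% | 3.150% | 6.0 points | 102.5 | 79.8% |
| 10% | 2.70% | 2.835% | 5.4 points | 114.3 | 75.4% |
| 25% | 2.25% | 2.3625% | 4.5 points | 137.8 | 67.4% |

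**The case against.** **The timing conflict may be narrower than it looks.** The exception in 5.7.1.3 follows a paragraph on pre-enrollment testing and can be read as confined to it. The sentence in 5.9.1.2 also sits in a discussion of diagnoses made before enrollment. Section 5.7.2.1 could be shorthand for the same rule. This has some force for the first two places, but 5.7.2.1 carries no such limit, and case (b) survives either reading.

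**The bias is hypothetical.** A reader might infer that the rule will give the cohorts different prevalences. The protocol does not support that. Nowhere does it say that screening differs between cohorts, and section 5.9.2 plans to recruit Cohort B from the same centers with the same strategies. This objection stands.

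**One case could reverse the result.** With 6/204 in B1, the Wald upper bound is 5.4 points at 4/102 and 6.75 points at 5/102, so it is tempting to say that one misclassified pregnancy flips the conclusion. But that is a property of 102 outcomes and would hold for any single case under any rule. It does not measure this defect.

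**Known positives leave while known negatives stay.** That reading is too broad. Subgroup 3 keeps abnormal results unrelated to aneuploid or genetic disorders, so only the aneuploid and genetic positives leave.

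**Sensitivity analyses are planned.** Tables 5 and 6 list several analyses by testing status and result, and 5.9.1.2 stratifies outcomes by the timing of enrollment relative to test results. These could expose an effect, but they do not settle who is in the primary set.

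**Conclusion.** The contradiction is established from the text alone: the sections disagree on whether the result must precede enrollment and on which tests count, and cases (a) and (b) fall on opposite sides. It is also established that the operative criterion is test type or timing while the stated reason is aetiology.

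The size of any bias is not established. At about 0.1-0.2 points, in either direction, it is small against the margin, and it rests on an assumed genetic share and an assumed imbalance in testing. The reason to act is that the primary set of a non-inferiority safety comparison with about nine expected cases should be fixed by one rule before any case is seen.

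**What to change.** State one rule and apply it identically to Groups 1, 2 and 3, whatever the test or its date. The blinded Adjudication Committee, whose listed expertise includes clinical genetics, labels each major malformation as chromosomal or monogenic, or neither. The primary numerator counts those that are neither. All major malformations are reported as a sensitivity analysis, which also serves the MACDP and EUROCAT comparison. Align 5.7.1.3, Table 5, 5.7.2.1, 5.7.4.2 and 5.9.1.2.

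Cost: one field on the adjudication form, the wording changes, and slightly fewer primary cases. Section 5.5.1 must also be reworked, because its 3% includes genetic defects. P_B1 has to be matched to the rule and the power restated. With the margin still tied to a risk ratio of 3.0 and a genetic share of 10-25%, about 114-138 Cohort A outcomes are needed instead of 102. If 102/204 is kept, power falls to roughly 75-67%. The genetic share is an assumption here, and the sponsor should replace it with a sourced figure.
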